## 9.4. Deaths, Serious Adverse Events and other Significant Adverse Events

The following listings will be presented including Participant ID, Adverse Event Description, Last Dose Received/Days Post Dose, Reason Reported as an SAE, Relationship to Treatment, Alternate Etiology if not Related, Outcome, and Duration of Event (days):

- Deaths and Serious Adverse Events ([Table 138](#));

## 9.5. Pregnancies

For any participants in the Safety population who became pregnant during the study, every attempt was made to follow the participants to completion of pregnancy to document the outcome, including information regarding any complications with pregnancy and/or delivery. Listings of pregnancies and outcomes will be presented (Listing 28, Listing 29, Listing 30, Listing 31, and Listing 32).

## 9.6. Clinical Laboratory Evaluations

The baseline value will be defined as the last value obtained prior to the first vaccination/dose of study product. If a participant has repeated laboratory values on the same day, the value from the last evaluation will be used for analysis. Post-baseline, in the case of multiple observations (for example, from supplemental visits), the assessment value that is closest to the scheduled visit window will be used in the analyses. All the recorded data will be listed. If observations have the same distance to the scheduled assessment, the latest one will be used.

Chemistry parameters evaluated were creatinine, ALT, Albumin, and Total Bilirubin. Hematology parameters evaluated were WBC, ANC, hemoglobin, and platelets.

All clinical laboratory parameters were evaluated at baseline (screening visit) and Day 57 for Oral and Sublingual Cohorts and at baseline (screening visit) and Day 71 for Intradermal Cohorts. ALT creatinine, and total bilirubin were also evaluated at Day 36 for Oral and Sublingual Cohorts and at Day 50 for Intradermal Cohorts. The distribution of laboratory results by severity, time point, and treatment group will be presented in [Table 142](#), [Table 143](#), [Table 144](#), [Table 145](#), and [Table 146](#) for chemistry and in [Table 151](#), [Table 152](#), [Table 153](#), [Table 154](#), and [Table 155](#) for hematology. Descriptive statistics including mean, standard deviation, median, minimum and maximum values and changes from baseline by time point, for each laboratory parameter, will be summarized in [Table 147](#), [Table 148](#), [Table 149](#), and [Table 150](#) for chemistry and in [Table 156](#), [Table 157](#), [Table 158](#), and [Table 159](#) for hematology. Changes in laboratory values will be presented beginning at [Figure 254](#) and concluding with [Figure 276](#).

Grading scales for safety laboratory parameters are presented in [Table 8](#).

[Listing 23](#) and [Listing 24](#) will provide a complete listing of individual clinical laboratory results with applicable reference ranges. [Table 140](#) and [Table 141](#) will provide a listing of only abnormal individual clinical laboratory results.

## 9.7. Vital Signs and Physical Evaluations

The baseline value will be defined as the last value obtained prior to the first vaccination/dose of study product. If a participant has repeated vital sign measurements on the same day, the value from the last evaluation will be used for analysis. Post-baseline, in the case of multiple observations (for example, from supplemental visits), the assessment value that is closest to the scheduled visit window will be used in the analyses. All the recorded data will be listed. If observations have the same distance to the scheduled assessment, the latest one will be used.

Vital sign measurements include systolic blood pressure, diastolic blood pressure, pulse, and oral temperature. Grading scales for vital signs are presented in [Table 9](#). Vital signs were assessed at Day 1, Day 8, Day 15, Day 22, Day 29, Day 36, Day 57, Day 114 and Day 209 for Oral and Sublingual Cohorts and at Day 1, Day 8, Day 22, and Day 29 for Intradermal Cohorts. Vital signs will be tabulated by severity, visit, and treatment group ([Table 160](#), [Table 161](#), [Table 162](#), [Table 163](#), and [Table 164](#); [Listing 25](#)).

Physical Examinations were performed at screening to assess general wellness. The following body systems were assessed: head, eyes, ears, nose, and throat; lymph nodes; skin; pulmonary; cardiovascular; abdominal; neurological; and musculoskeletal systems. At subsequent visits including enrollment a targeted physical examination was conducted if indicated based on review of medical history. Findings will be presented in Listing 26.

## **9.8. Concomitant Medications**

Concomitant medications will be coded to the Anatomical Therapeutic Classification using the WHO Drug Dictionary. The use of prior and concomitant medications taken during the study was recorded on the CRFs. A by-participant listing of concomitant medication use will be presented (Listing 27).

## **9.9. Other Safety Measures**

Not applicable.

## **10. PHARMACOKINETICS**

Not applicable.

## **11. IMMUNOGENICITY**

See Section [8](#).

## **12. OTHER ANALYSES**

Not applicable.

### **13. REPORTING CONVENTIONS**

The mean, standard deviation, and other statistics will be reported to 1 decimal place greater than the original data. The minimum and maximum will use the same number of decimal places as the original data.

Proportions will be presented as 2 decimal places; values greater than zero but <0.01 will be presented as “<0.01”. Percentages will be reported to the nearest whole number; values greater than zero but < 1% will be presented as “<1”; values greater than 99% but less than 100% will be reported as >99%.

## **14. TECHNICAL DETAILS**

SAS version 9.4 or above will be used to generate all tables, figures and listings.

---

**15. SUMMARY OF CHANGES IN THE CONDUCT OF THE STUDY OR PLANNED ANALYSES****Changes to Study Conduct**

- At the request of the local (icddr,b) DSMB, collection of serum bilirubin at screening and Visit 6 and collection of ALT and creatinine at Visit 6 were added to the safety labs. These results were not obtained for Cohorts A through C which were enrolled prior to the request.
- Due to a country-wide lockdown instituted in Bangladesh to combat the COVID-19 pandemic all Cohort E participants did not receive a third dose of study product. Cohort D participant Visits 8 and 9 and Cohort E participant Visits 6 through 9 were not conducted and no further cohorts were enrolled due to the pandemic.

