##### Secondary

- To assess the long-term safety, from first vaccination through 6 months following the last dose of vaccine
- To evaluate the serum anti-dmLT Immunoglobulin IgG and IgA response
- To evaluate the IgG and IgA anti-dmLT Antibody Secreting Cell (ASC) response
- To evaluate the IgG and IgA anti-dmLT Antibodies in Lymphocyte Supernatant (ALS) response
- To evaluate the total fecal IgA and fecal anti-dmLT IgA response
- To evaluate the total salivary IgA and the saliva-derived anti-dmLT IgA response

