##### 3.2.2. Secondary Outcome Measures

The **Secondary Safety Endpoints** to be used to evaluate the safety of this study are:

- The occurrence of vaccine-related serious adverse events (SAE) from the first vaccination through 6 months after the last dose of vaccine was administered
-

The **Secondary Immunogenicity Endpoints** to be used to evaluate the immune response to vaccination consist of the following:

- At any time after vaccination, the proportion of participants with a  $\geq 4$ -fold rise in dmLT-specific serum IgG and IgA titers over baseline measured by Enzyme-Linked Immunosorbent Assay (ELISA)
- At any time after vaccination the proportion of participants with  $\geq 8$  dmLT-specific IgA or IgG ASC /  $10^6$  peripheral blood mononuclear cells (PBMC) as measured by Enzyme-Linked ImmunoSpot Assay (ELISpot)
- At any time after vaccination, the proportion of participants with  $\geq 2$ -fold rise in ALS anti-dmLT-specific IgG and IgA titers over baseline measured by ELISA
- At any time after vaccination, the proportion of participants with a  $\geq 4$ -fold rise over baseline in dmLT-specific fecal IgA titers measured by ELISA
- At any time after vaccination, the proportion of participants with a  $\geq 4$ -fold rise over baseline in dmLT-specific salivary IgA titers measured by ELISA

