#### **4.5.1. Safety Variables**

Safety, reactogenicity, and tolerability will be assessed by:

1. Frequency and Severity of Solicited Adverse Events – reactogenicity events occurring from vaccination through 7 days after each dose of vaccine is administered:
  - a) Local solicited events include: irritation of the oral cavity or tongue, diarrhea, nausea, vomiting, and abdominal discomfort for Oral Cohorts; irritation of the oral cavity or tongue, facial nerve disturbance, diarrhea, nausea, vomiting, or abdominal discomfort for Sublingual Cohorts; and injection site pain, redness, swelling, bruising, itching, hypo/hyper pigmentation and induration, vesicles or hardened mass for Intradermal Cohorts.
  - b) Systemic solicited events include: fever, feverishness, fatigue, malaise, myalgia, or headache for Oral and Sublingual Cohorts; and fever, feverishness, fatigue, malaise, myalgia, headache, diarrhea, nausea, vomiting, or abdominal discomfort for Intradermal Cohorts.
2. Frequency of participant withdrawals from first vaccination through the end of follow-up (Day 209 for Oral and Sublingual Cohorts, Day 223 for Intradermal Cohorts)
3. Frequency of discontinuation of study vaccination during the study

4. Frequency and severity of unsolicited vaccine-related non-serious adverse events (AE), including laboratory AE, from first vaccination through 28 days after the last dose of vaccine is administered (Day 57 for Oral and Sublingual Cohorts, Day 71 for Intradermal Cohorts)
5. Frequency of vaccine-related SAEs from the first vaccination through the end of follow-up (Day 209 for Oral and Sublingual Cohorts, Day 223 for Intradermal Cohorts)

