## 9.3. Adverse Events

When calculating the incidence of adverse events (i.e., on a per participant basis), each participant will only be counted once and any repetitions of adverse events within a participant will be ignored; the denominator will be the total population size. All adverse events reported will be included in the summaries and analyses.

An overall summary of adverse events by treatment group is presented in [Table 91](#) and [Table 92](#). Unsolicited adverse events occurring in more than 5% of participants in any treatment group are presented in [Table 93](#) and [Table 94](#).

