**Table 90: Correlation of ASC IgG Count vs ALS IgG Titers GMFR by Time Point and Treatment Group, Per Protocol Population**

## 14.3 Safety Data

### 14.3.1 Displays of Adverse Events

**Table 91: Overall Summary of Adverse Events - Oral & Sublingual Cohorts**

	Cohort A: Oral 5 µg dmLT (N=X)		Cohort B: Oral 25 µg dmLT (N=X)		All Oral Cohorts: Placebo (N=X)		All Oral Route Subjects (N=X)		Cohort C: Sublingual 5 µg dmLT (N=X)		Cohort D: Sublingual 25 µg dmLT (N=X)		All Sublingual Cohorts: Placebo (N=X)		All Sublingual Route Subjects (N=X)	
Subjects a with	n	%	n	%	n	%	n	%	n	%	n	%	n	%	n	%
At least one local solicited adverse event	x	x	x	x	x	x	x	x	x	x	x	x	x	x	x	x
At least one systemic solicited adverse event	x	x	x	x	x	x	x	x	x	x	x	x	x	x	x	x
At least one unsolicited adverse event	x	x	x	x	x	x	x	x	x	x	x	x	x	x	x	x
At least one related unsolicited adverse event, through 28 days after the last dose	x	x	x	x	x	x	x	x	x	x	x	x	x	x	x	x
Mild (Grade 1)	x	x	x	x	x	x	x	x	x	x	x	x	x	x	x	x
Moderate (Grade 2)	x	x	x	x	x	x	x	x	x	x	x	x	x	x	x	x
Severe (Grade 3)	x	x	x	x	x	x	x	x	x	x	x	x	x	x	x	x
Not yet assessed																
At least one related unsolicited adverse event, from first vaccination through 6 months after the last dose	x	x	x	x	x	x	x	x	x	x	x	x	x	x	x	x
Mild (Grade 1)	x	x	x	x	x	x	x	x	x	x	x	x	x	x	x	x
Moderate (Grade 2)	x	x	x	x	x	x	x	x	x	x	x	x	x	x	x	x
Severe (Grade 3)	x	x	x	x	x	x	x	x	x	x	x	x	x	x	x	x
Not yet assessed																

	Cohort A: Oral 5 µg dmLT (N=X)		Cohort B: Oral 25 µg dmLT (N=X)		All Oral Cohorts: Placebo (N=X)		All Oral Route Subjects (N=X)		Cohort C: Sublingual 5 µg dmLT (N=X)		Cohort D: Sublingual 25 µg dmLT (N=X)		All Sublingual Cohorts: Placebo (N=X)		All Sublingual Route Subjects (N=X)	
Subjects a with	n	%	n	%	n	%	n	%	n	%	n	%	n	%	n	%
At least one severe (Grade 3) unsolicited adverse event	x	x	x	x	x	x	x	x	x	x	x	x	x	x	x	x
Related	x	x	x	x	x	x	x	x	x	x	x	x	x	x	x	x
Unrelated	x	x	x	x	x	x	x	x	x	x	x	x	x	x	x	x
At least one serious adverse event b	x	x	x	x	x	x	x	x	x	x	x	x	x	x	x	x
At least one related, serious adverse event	x	x	x	x	x	x	x	x	x	x	x	x	x	x	x	x
At least one adverse event leading to early termination c	x	x	x	x	x	x	x	x	x	x	x	x	x	x	x	x
Study withdrawal for any reason	x	x	x	x	x	x	x	x	x	x	x	x	x	x	x	x
Discontinuation of study vaccination for any reason	x	x	x	x	x	x	x	x	x	x	x	x	x	x	x	x

N = Number of subjects in the Safety Population

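### The related-SAE percentages meant to answer the 6-month safety objective divide by the full Safety Population, although Cohorts D and E had no scheduled SAE assessment near 6 months

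*SAP*

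**What the plan says.** The secondary safety objective in SAP 3.1 is "To assess the long-term safety, from first vaccination through 6 months following the last dose of vaccine". The one secondary safety endpoint, in SAP 3.2.2, is "The occurrence of vaccine-related serious adverse events (SAE) from the first vaccination through 6 months after the last dose of vaccine was administered". SAP 4.5.1 turns this into "Frequency of vaccine-related SAEs from the first vaccination through the end of follow-up" and sets the end at Day 209 for oral and sublingual cohorts and Day 223 for intradermal cohorts.

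For adverse event incidence, SAP 9.3 says that "the denominator will be the total population size". Table 91 has a row "At least one related, serious adverse event" shown as n and %, with the note "N = Number of subjects in the Safety Population". Table 92 repeats the layout for Cohort E and adds an All Subjects column. SAP 6.3.1 admits to the Safety Population any eligible participant who received at least one dose.

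SAP 15 then reports that, because of the pandemic, "Cohort D participant Visits 8 and 9 and Cohort E participant Visits 6 through 9 were not conducted", and that no Cohort E participant received the third dose.

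**The concern.** Under the protocol (Sections 7.3.7 and 7.4.1, Appendix A), the scheduled SAE reviews after Visit 7 are at Visits 8 and 9. Those visits did not take place for Cohort D, and Cohort E lost Visit 6 as well. A participant with no recorded SAE and no later contact still enters the denominator, and so counts as free of related SAEs for the whole period through Day 209 or 223.

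The error runs in the reassuring direction, on the trial's only long-term safety endpoint. It falls entirely on the highest sublingual dose given and on the only intradermal group. Zero related SAEs in those columns would look the same as zero in the oral columns, where the 6-month visits were not cancelled.

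The SAP adapted other displays to the same loss. The vital-sign shell (Table 160) omits Cohort D at 85 and 180 days after dose 3 and omits Cohort E after the post-dose-2 visit. The chemistry shell (Table 142) drops Cohort E from the post-dose-3 rows and carries a Missing column. The SAE rows received no such change, and SAP 15 lists changes in conduct but none in analysis.

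**Working it through.** **Inputs**
- Enrolment per cohort: 12 dmLT and 3 placebo (SAP 4.4.3). Cohorts enrolled: A to E (SAP 4.1).
- Cohort D: dose 3 on Day 29; last visit not listed as cancelled is Visit 7, Day 57 (SAP Table 2, SAP 15).
- Cohort E: last dose is dose 2, Day 22 (SAP 4.4.5). The last assessment listed is Day 29 (vital signs, SAP 9.7). Visit 5, Day 43, is not listed as cancelled, so it is the latest possible scheduled contact.

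**Days observed after the last dose, against about 180 planned** (209 − 29 = 180; 223 − 43 = 180)
- Cohort D: 57 − 29 = 28 days; 28/180 = 16%.
- Cohort E: 29 − 22 = 7 days; 7/180 = 4%. If Visit 5 was held, 43 − 22 = 21 days; 21/180 = 12%. Either way Cohort E falls short of even the 28-day window.

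**Share without a scheduled 6-month assessment, at target enrolment**
- All Subjects: (15 + 15)/75 = 30/75 = 40%.
- All Sublingual Route Subjects (C and D): 15/30 = 50%.
- Sublingual 25 µg dmLT, intradermal 0.3 µg dmLT and intradermal placebo columns: 100%.

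The SAP does not list actual group sizes. Among vaccinees the target share is 24/60 = 40%. With 10 per cohort it is 20/50 = 40%. With 10 in each of A-D (the 40 vaccinees in SAP 5) and 12 in E, it is 22/52 = 42.3%. With 10 in D and 12 elsewhere, it is 22/58 = 37.9%. The share therefore stays between 38% and 42%.

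**Reproducing the plan's precision method.** SAP 5 gives exact upper bounds for zero events. The two-sided 95% Clopper-Pearson limit is U(n) = 1 − 0.025^(1/n). It gives U(10) = 30.8%, U(20) = 16.8%, U(40) = 8.8% and U(60) = 6.0%, matching all four figures. The one-sided version (25.9%, 13.9%, 7.2%, 4.9%) does not match.

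**The same formula on the SAE columns, assuming zero related SAEs.** The tables print no confidence interval for these rows, so this is an illustration of the information they carry.

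| Column | Denominator per SAP | U(n) | Cohorts with Visits 8-9 only | U(n) |
|---|---|---|---|---|
| All Subjects | 0/75 | 4.8% | 0/45 (A-C) | 7.9% |
| All Sublingual | 0/30 | 11.6% | 0/15 (C) | 21.8% |
| Sublingual 25 µg dmLT | 0/12 | 26.5% | none | no estimate |
| Intradermal 0.3 µg dmLT | 0/12 | 26.5% | none | no estimate |

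One related SAE in Cohorts A-C would be 1/75 = 1.3% under the SAP rule and 1/45 = 2.2% among those cohorts.

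**The case against.** **SAEs could have been captured in other ways.** The protocol provides for SAE review at unscheduled visits (7.6) and early termination visits (7.5), telephone contact for early withdrawals (5.3.4), and site reporting of SAEs, including suspected related ones learned of after the study (9.3.1). Protocol 9.6.1 also expects safety follow-up visits to continue if the study is discontinued. This stands. A reader might infer that nobody observed Cohorts D and E after these visits stopped, but the documents show only that scheduled visits were missed. Equally, neither document says that any of these routes was used for D or E, and passive reporting does not establish that a participant was SAE-free at 6 months.

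**The row carries no time label, and SAEs will be listed individually.** Also true: the related-SAE row in Table 91 has no window, and Table 138 lists each SAE with days post dose. But SAP 4.5.1 defines the endpoint as a frequency through Day 209/223, and no other row reports it. A separate Table 91 row, for related unsolicited events, is explicitly labelled through 6 months and has the same denominator. A listing of events cannot show who was not followed.

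**The loss is disclosed.** SAP 15, the completed-follow-up line of Tables 10-11, the CONSORT figures and Listing 1 show it. They let a careful reader discount the SAE percentage, but they do not correct it.

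**SAP 6.1 bases percentages on the non-missing sample size.** That general rule would help, but SAP 9.3 is specific to adverse events and the Table 91 note agrees with it. The two rules need reconciling.

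**Stated bounds.** A reader might also infer that the 6.0% bound in SAP 5 is undermined, or that the tables will print 0/60 vaccinees. Neither follows. The 6.0% is a planning figure for dose-limiting AEs in Cohorts A-F at the review 7 days after dose 3, no vaccinee-only pooled column exists, and the documents state no bound for 6-month SAEs.

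**Conclusion.** The concern holds in this form: as written, the SAP produces related-SAE percentages for the 6-month objective in which about 40% of participants overall, half of the sublingual route column, and everyone in the sublingual 25 µg and intradermal columns had no scheduled assessment near 6 months. For those last groups the objective has no documented answer. For the pooled columns the zero-event upper limit moves from 4.8% to 7.9% (All Subjects) and from 11.6% to 21.8% (All Sublingual).

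This rests on three assumptions: enrolment at target (the share is robust to the alternatives shown), Cohorts A-C completing Visits 8 and 9, and no SAE ascertainment in D and E beyond what the documents record. If contacts of equal length were made and documented, those participants belong back in the denominator. The trial tests no hypothesis, so no formal inference is affected. What changes is which groups can support a 6-month safety statement.

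**What to change.** 1. In SAP 9.3 and 9.4 and Tables 91-92 and 95-96, report SAEs through the last completed contact for all participants, with follow-up duration per group.
2. Report a separate row for related SAEs through 6 months, with the denominator limited to participants whose status is known at Visit 9 or at a documented contact of equal length. Apply the same restriction to the Table 91 row for related unsolicited events through 6 months. Enter *not assessed* for Cohorts D and E unless such contact exists.
3. Reconcile the total-population rule in SAP 9.3 with the non-missing rule in SAP 6.1.
4. State in SAP 4.5.1 and 9.4 that, absent such contact, the 6-month objective is evaluable only for oral 5 µg, oral 25 µg, sublingual 5 µg and the placebo recipients of those cohorts. Record the change in SAP 15.

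A person-time rate is optional and adds little with groups of about 12 and few expected events.

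The cost is SAP wording and a few table rows, plus a check of whether any later contact with D and E was documented. No new data collection is needed. The downside is smaller denominators and no 6-month result for two dose groups.

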## **17. LISTING OF TABLES, FIGURES, AND LISTINGS**

Table, figure, and listing shells are presented in Appendices 1, 2, and 3.

## 9.1 Overall Study Design and Plan Description

**Table 1: Study Design**

Cohort	Group	Route	dmLT dose (µg)	Target No. Participant Enrollment	Minimum No. Participants Evaluable*	Vaccination Days
A	A1 A2	Oral	5 placebo	12 3	10 1	1, 15, 29
ISM, MM, and the protocol PI will review Cohort A safety data collected through 7-days post vaccination of third dose of last participant for recommendation to proceed to the cohort B.						
B	B1 B2	Oral	25 placebo	12 3	10 1	1, 15, 29
ISM, MM, and the protocol PI will review Cohort C safety data collected 7-days post vaccination of third dose of last participant for recommendation to proceed to the cohort D.						
C	C1 C2	Sublingual	5 placebo	12 3	10 1	1, 15, 29
ISM, MM, and the protocol PI will review Cohort C safety data collected 7-days post vaccination of third dose of last participant for recommendation to proceed to the cohort D.						
D	D1 D2	Sublingual	25 placebo	12 3	10 1	1, 15, 29
E a	E1 E2	Intradermal	0.3 placebo	12 3	10 1	1, 22, 43
ISM, MM, and the protocol PI will review Cohort E safety data collected through 7-days post vaccination of third dose of last participant for recommendation to proceed to the cohort F.						
F b	F1 F2	Intradermal	1.0 placebo	12 3	10 1	1, 22, 43
Scheduled DMID DSMB meeting will be held to review cumulative safety data through 7 days after the third dose of vaccine and determine if study should proceed to Cohorts G, H and I.b						
G b	G1 G2	Oral	50 placebo	12 3	10 1	1, 15, 29
H b	H1 H2	Sublingual	50 placebo	12 3	10 1	1, 15, 29
I b	I1 I2	Intradermal	2.0 placebo	12 3	10 1	1, 22, 43
Scheduled DMID DSMB meeting will be held to review the aggregate safety data through 28 days after the third dose of vaccine for all nine cohorts (A-I)b						
A Final DMID DSMB meeting will be held to review the safety data following the completion of the study						

a Halted prior to Dose 3 because of COVID-19 Pandemic

b Not done due to COVID-19 Pandemic

